2.5 Analysis supporting primary objective(s)

The primary objective is to assess the effect on LDL-C of an "inclisiran-first" implementation strategy compared to usual care at Day 330 in participants with ASCVD and an LDL-C \geq 70 mg/dL despite maximally tolerated statin therapy and to assess the non-inferiority of an "inclisiran first" implementation strategy compared to usual care on discontinuation of background statin therapy at Day 330.

2.5.1 Primary endpoint(s)

The primary efficacy variables are the following:

1. Percent change from baseline in LDL-C
2. Discontinuation of statin therapy (i.e., no statin use \geq 30 days before the end-of-study visit) (yes, no)

The primary analysis time point for both primary efficacy variables is at Day 330.

The following provides additional details on the derivation of primary efficacy variable 2.

If a participant is considered a study completer and has a non-missing visit date for the nominal Day 330 visit recorded, a statin assessment date (to assess if the participant was taking statins at this point in time) will be calculated by subtracting 30 days from the Day 330 visit date (e.g., study Day 300 if the participant completes on study Day 330). The statin assessment date will be compared to the maximum statin end date of all statin medications taken by the participant. If the last statin is recorded as ongoing at study end date, the maximum statin end date will be set to the study end date.

- If the participant was on a statin on or after this statin assessment day (maximum statin end date \geq statin assessment date), the participant will be considered as discontinued statin = 'no.'
- If the participant was not on a statin on and after this statin assessment day (maximum statin end date $<$ statin assessment date), or they were a completer who did not have a Day 330 visit, the participant will be considered as discontinued statin = 'yes.'

All early termination participants will be considered to not be on a statin for this endpoint (the participant will be considered as discontinued statin = 'yes').

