## **9.2 Study completion and post-study treatment**

At the study completion/end of study visit, including participants who are prematurely withdrawn from the study, the referring or primary physician will continue to provide ongoing medical care. When the participant has completed all scheduled study assessments, the investigator must call the IRT to record the participant completion in the IRT.

Study completion is defined as when the last participant finishes their Study Completion Visit and any repeat assessments associated with this visit have been documented and followed-up appropriately by the Investigator or, in the event of an early study termination decision, the date of that decision (e.g. Each participant will be required to complete the study in its entirety and thereafter no further study treatment will be made available to them).

For study participants who have successfully completed the study/treatment epoch, further guidance will be provided separately concerning continuation of treatment and access to investigational drug. This guidance will be provided to sites prior to the completion visit of the first patient (first patient last visit). For study participants who terminate prior to the end of the treatment epoch or who withdraw from treatment, continuing treatment should be managed by the investigator and/or referring physician.

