## **12.4 Analysis supporting primary objectives**

### **12.4.1 Definition of primary endpoints**

The primary efficacy variables are the following:

1. Percent change from baseline in LDL-C
2. Discontinuation of statin therapy (i.e., no statin use  $\geq 30$  days before the end-of-study visit) (yes, no)

The primary analysis time point for both primary efficacy variables is at Day 330.

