2.1.1 General definitions

Study Treatment

The following are the investigational treatments:

- Inclisiran (KJX839), 284 mg, 1.5 ml liquid in a single-use prefilled syringe (PFS) for s.c. administration plus usual care
- Usual care alone

The following treatment labels will be used for all tables, listings and figures:

- Inclisiran First
- Usual Care

Study treatment start and end date

Study treatment start date is defined as the first date when a non-zero dose of study drug is administered for the inclisiran group. If a participant, who is randomized to the Inclisiran First group, does not take any study drug then treatment start date will be the randomization date.

For the usual care alone group the study treatment start date will be the randomization date.

“Day 1” will be used to identify study treatment start date for both treatments.

Study treatment end date is defined as the treatment phase completion date recorded on the “Treatment Disposition” CRF for inclisiran participants. For the usual care alone group, the study treatment end date is the last recorded contact/participation date in the database.

Study start and end date

Study start date is defined as the first date when a non-zero dose of study drug is administered for the inclisiran group. If a participant, who is randomized to the Inclisiran First group, does not take any study drug then study start date will be the randomization date.

For the usual care alone group the study start date will be the randomization date.

Study end date is defined as the date of last recorded contact/participation date in the database.

Planned and actual treatment definitions

Table 2-1 Planned and Actual Treatment Definitions

Randomized Treatment Group	Inclisiran Use Scenario During Study (Inclisiran Use Recorded as Study Treatment or Concomitant Medication)	Planned Treatment	Actual Treatment
Inclisiran First	Received at least one dose of inclisiran	Inclisiran First	Inclisiran First
Inclisiran First	Never received inclisiran	Inclisiran First	Usual Care
Usual Care	Received at least one dose of inclisiran	Usual Care	Inclisiran First
Usual Care	Never received inclisiran	Usual Care	Usual Care

Study day

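### The statin-discontinuation rule checks only the latest statin end date, so a statin first restarted on or after the Day 330 visit codes a completer who was off statin as 'not discontinued'

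*SAP*

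**What the plan says.** SAP 2.5.1 words the endpoint as "Discontinuation of statin therapy (i.e., no statin use" for at least 30 days before the end-of-study visit. Protocol 12.4.1 fixes the time: "The primary analysis time point for both primary efficacy variables is at Day 330".

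For a completer with a recorded Day 330 visit, SAP 2.5.1 sets an assessment date 30 days before that visit, with the stated aim "to assess if the participant was taking statins at this point in time". The rule is then: "The statin assessment date will be compared to the maximum statin end date of all statin medications taken by the participant". The result is 'no' (not discontinued) if the maximum end date is on or after the assessment date, and 'yes' otherwise. The accompanying prose is just as open-ended: "If the participant was on a statin on or after this statin assessment day".

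For open records: "If the last statin is recorded as ongoing at study end date, the maximum statin end date will be set to the study end date". SAP 2.1.1 adds: "Study end date is defined as the date of last recorded contact/participation date in the database". That date need not be the Day 330 visit date.

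Early terminators, and completers without a Day 330 visit, are coded 'yes' whatever their statin records show.

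**The concern.** The endpoint definition closes its window at the visit. The derivation does not: it uses no statin start date and has no upper limit. A statin that begins on the visit day or later has an end date after the assessment date, so it overrides any earlier period off statin.

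Such records can reach the database. Concomitant medications are collected at Visit 6 (Protocol Table 8-1). SAP 2.4.2 puts no upper date on concomitant medication, and SAP 5.1.3 uses complete end dates as recorded. SAP 1.1 says eCRF data will be complemented by EHR and claims data. After the study, "the referring or primary physician will continue to provide ongoing medical care" (Protocol 9.2).

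The SAP does limit dates elsewhere. The statin-intensity shift table in SAP 2.4.2 uses the last statin taken up to Day 330, and secondary variable 22 uses intensity on the nominal visit date. A participant who restarts on day 340 would have intensity 'none' at Day 330 for variable 22, yet count as not discontinued for the primary endpoint.

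At stake is the count of events in a primary non-inferiority comparison. The error runs only from 'yes' to 'no'.

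**Working it through.** **1. The plan's own figure.** Inputs from SAP section 3: proportion 0.20 in each arm, margin 0.15, one-sided alpha 0.0125, power 0.90.

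n per arm = (2.2414 + 1.2816)² × 2 × 0.20 × 0.80 / 0.15² = 176.5, rounded up to 177, so 354 in total. This matches Table 3-2. The sample size is not in question.

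**2. The rule applied literally.** Day 330 visit on study day 330, assessment date day 300. The last column codes 'no' only if some record starts before the visit and ends (or is ongoing) on or after day 300.

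| Statin history | SAP rule | With start-date condition |
|---|---|---|
| Continuous | no | no |
| Stopped day 100, no restart | yes | yes |
| Stopped day 100, restarted day 315, ongoing | no | no |
| Stopped day 100, restarted day 330, ongoing | no | yes |
| Stopped day 100, restarted day 340, ongoing | no | yes |
| Stopped day 100, restarted day 340, ended day 344 | no | yes |

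In the last three rows the participant was off statin for 330 − 100 = 230 days before the visit. The day-315 restart is correctly 'no', because it falls inside the 30-day window. Capping end dates at the visit changes none of these results: a capped date of 330 is still on or after 300.

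**3. Illustration of size.** The documents give no restart rate, so the share f below is an assumption.

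- Arm size: 222 × 0.90 = 199.8, about 200. SAP 2.5.2 excludes participants with a history of statin intolerance (planned at 10%) and keeps early terminators.
- True rates at the margin: 0.35 (inclisiran-first) and 0.20 (usual care).
- Early terminators: 0.10 of each arm, the planned loss to follow-up. They are always 'yes' and cannot be recoded. That leaves 0.25 and 0.10 exposed.
- Chance of declaring non-inferiority = Φ[(0.15 − d)/SE − 2.2414], where d is the coded difference and SE = √[p₁(1−p₁)/200 + p₂(1−p₂)/200].

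Inclisiran arm only, f = 5%: p₁ = 0.10 + 0.25 × 0.95 = 0.3375, d = 0.1375, SE = 0.0438. Then Φ(0.0125/0.0438 − 2.2414) = Φ(−1.956) = 0.025.

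Inclisiran arm only, f = 10%: p₁ = 0.325, d = 0.125, SE = 0.0436. Then Φ(0.574 − 2.2414) = 0.048.

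| f | Inclisiran arm only | Both arms equally | Usual care only |
|---|---|---|---|
| 0% | 0.0125 | 0.0125 | 0.0125 |
| 1% | 0.014 | 0.014 | 0.012 |
| 2% | 0.017 | 0.015 | 0.011 |
| 5% | 0.025 | 0.019 | 0.009 |
| 10% | 0.048 | 0.029 | 0.007 |

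In head-counts, the exposed inclisiran group is 0.25 × 200 = 50 people, so 5% and 10% mean 2.5 and 5 participants.

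**The case against.** The strongest reply is that the case will rarely arise. Visit 6 is the last scheduled visit and the last scheduled collection of medications. Only SAE reporting runs on, for 30 days (Protocol 10.1.3). For most completers the last recorded contact should be Visit 6 itself. Protocol 11.1 makes EHR and claims capture conditional, and neither document says that records after Visit 6 will be drawn. This stands: the most realistic case is a statin start dated on the visit day, and the frequency may be close to zero.

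It can also be said that the intent is clear, since the SAP speaks of status at a point in time and of Day 330. That is true, but the programmed comparison does not follow the intent, and the sentence beside it is equally open-ended.

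A reader might infer that the error favours inclisiran, because sponsor supply ends with the study and could prompt statin restarts in that arm. The documents do not support this. Protocol 9.2 is mixed: it says no further study treatment will be available, but also that guidance on continued treatment and access will follow separately. Inclisiran is commercially available. The last dose is on Day 270 and later doses are six-monthly (Protocol 6.5), so none falls due at Day 330. LDL-C results reach the physicians of both arms (Protocol section 3), so a restart in usual care is just as conceivable.

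A reader might also apply f to the whole 0.35, which gives 0.033 and 0.076 for 5% and 10%. That overstates the effect, because early terminators stay 'yes' under SAP 2.5.1.

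**Conclusion.** The rule is wrong as written. For a completer with a Day 330 visit, off statin for more than 30 days before it and with a statin start recorded on or after the visit date, SAP 2.5.1 returns 'no' where the endpoint definition gives 'yes'.

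The error only removes events. Equal removal in both arms shrinks a true difference towards non-inferiority, removal only in the inclisiran arm is anti-conservative, and removal only in usual care is conservative. Which applies is not shown, and no restart rate is given. The type I error figures therefore rest wholly on the assumed f, the 0.35 versus 0.20 rates and the 10-point share of early terminators. At f = 0 there is no effect. The point merits correction because it concerns a primary endpoint and is cheap to settle, not because a material bias has been demonstrated.

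**What to change.** In SAP 2.5.1, for completers with a Day 330 visit, code 'no' only if at least one statin record has both (a) a start date before the Day 330 visit date and (b) an end date, or ongoing status, on or after the Day 330 visit date minus 30 days. Otherwise code 'yes'. This also settles a statin started on the visit day.

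State how missing start dates are handled. SAP 5.1.3 does not impute them, so condition (a) read literally could turn a long-standing user into a discontinuer. Treat such a record as started before the visit if it is a baseline or prior statin, or was reported at an earlier visit.

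Do not rely on capping end dates at the visit. The start-date condition is the operative change.

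Cost: a short SAP revision before database lock, one further condition in the derivation program and the missing-date rule. No new data are needed and the sample size is unchanged.

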Since inclisiran is commercially available in the US as of late-2021, utilization of it in the usual care group at the sole discretion of the treating physician will not be encouraged, but will also not be prohibited to avoid withholding of appropriate care. If treatment with a PCSK9-inhibiting monoclonal antibody was initiated and a patient would have to be transitioned to inclisiran, the PCSK9-inhibiting monoclonal antibody should be discontinued.

The collection of data from trial sites through eCRFs will be complemented with EHR data and claims data (e.g., lipid measurements and concomitant medications).

Participants randomized to “inclisiran first” implementation strategy group will receive inclisiran at Day 0, Day 90 and Day 270, consistent with the dosing regimen studied in the Phase III trials.

While study visits will be preferentially performed in-person at the study sites, phone or virtual visits are an acceptable alternative if in-person visits are not permitted or impractical due to a Public Health Emergency. Site or home health nursing service may be used to assist with blood draws and/or study medication administration if required at these visits. Informed consent forms will be available in English and Spanish.

Figure 3-1 Study Design

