despite being treated with a combination of high intensity statin therapy and ezetimibe (Grundy et al 2019). Nonetheless, many patients still fail to reach acceptable LDL-C levels while being treated with a statin-ezetimibe combination due to the fact that ezetimibe lowers LDL-C by only ~20%. Therefore, addition of a more potent therapy without the disadvantages of PCSK9 inhibiting monoclonal antibodies, such as inclisiran, might be a valuable alternative to ezetimibe in patients with elevated LDL-C despite maximally tolerated statin therapy - i.e., an "inclisiran first" implementation strategy. Important considerations of the study design include:

**Recruitment:** Potentially eligible participants will be pre-screened using EHR, claims and/or laboratory databases. This will maximize the representativeness of the sample because it will reduce selection bias that occurs when investigators identify all participants by convenience sampling. Moreover, centrally identifying potential study sites and participants using EHR, claims and/or laboratory data will allow us to ensure that the study sites are representative while excluding sites that manage lipids more aggressively than is typical (for example specialized lipid clinics). Eligible participants will need to consent to having health records made available as part of the collection of medical and pharmacy claims. [REDACTED]

**Responsibilities of principal investigator / routine care physician:** Study visits will be done by the PI while routine care is performed by the participant's own treating physician. Communication and coordination between the PI and treating physician is allowed. However, PIs are asked to refrain from influencing treatment decisions that are usually made by the treating physician to maximize external generalizability (i.e., the influence of study participation on routine care should be as limited as possible). The PI and treating physician can be from the same practice.

**Open-label:** The study will be performed as an open-label study to mimic routine care decision-making, following from the primary objective of the study. For example, if the study would have been performed as a double-blind placebo-controlled study, it would not be possible to study the effect of inclisiran treatment on statin discontinuation as participants and investigators would not be aware of treatment allocation.

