## **9 Study discontinuation and completion**

### **9.1 Discontinuation and completion**

#### **9.1.1 Study treatment discontinuation and study discontinuation**

Discontinuation of study treatment for a participant occurs when study treatment is stopped earlier than the protocol planned duration and can be initiated by either the participant or the investigator.

The investigator must discontinue study treatment for a given participant if, he/she believes that continuation would negatively impact the participant's well-being.

Study treatment must be discontinued under the following circumstances:

- Participant/guardian decision
- Pregnancy
- Use of prohibited treatment as per recommendations in the prohibited treatment section
- Any situation in which study participation might result in a safety risk to the participant
- Any severe suspected drug related AE at the investigator's discretion

If discontinuation of study treatment occurs, the investigator should make a reasonable effort to understand the primary reason for the participant's premature discontinuation of study treatment and record this information.

Participants who discontinue study treatment or who decide they do not wish to participate in the study further should NOT be considered withdrawn from the study UNLESS they withdraw their consent (see 'Withdrawal of Informed Consent' section). **Where possible, they should return for the assessments indicated** in the Assessment Schedule. If they fail to return for these assessments for unknown reasons, every effort (e.g. telephone, e-mail, letter) should be made to contact the participant/pre-designated contact as specified in the lost to follow-up section. This contact should preferably be done according to the study visit schedule. Unless a participant withdraws informed consent, personal and coded data are able to be collected in accordance with the informed consent form.

If the participant cannot or is unwilling to attend any visit(s), the site staff should maintain regular telephone contact with the participant, or with a person pre-designated by the participant. This telephone contact should preferably be done according to the study visit schedule.

After study treatment discontinuation, at a minimum, in abbreviated visits, the following data should be collected at clinic visits or via telephone/email contact:

- New / concomitant treatments
- Adverse Events / Serious Adverse Events

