### 9.1.2 Withdrawal of informed consent

Participants may voluntarily withdraw consent to participate in the study for any reason at any time. Withdrawal of consent occurs only when a participant:

- Does not want to participate in the study anymore,

and

- Does not want any further study related contacts

In this situation, the investigator should make a reasonable effort (e.g. telephone, e-mail, letter) to understand the primary reason for the participant's decision to withdraw his/her consent and record this information.

Study treatment must be discontinued and no further assessments conducted, and the data that would have been collected at subsequent visits will be considered missing.

Further attempts to contact the participant are not allowed unless safety findings require communicating or follow-up.

All efforts should be made to complete the assessments prior to study discontinuation. A final evaluation at the time of the participant's study discontinuation should be made as detailed in the assessment table.

Novartis will continue to retain and use all research results (data) that have already been collected for the study evaluation.

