### 12.4.4 Handling of missing values not related to intercurrent event

For the primary analysis of primary efficacy variable 1, the MMRM implicitly imputes missing data under a missing at random assumption.

For the primary analysis of primary efficacy variable 2, participants for whom it cannot be ascertained that they are on statin therapy at the end of study will be assumed to have discontinued statin therapy.

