2.5.4 Handling of missing values not related to intercurrent event

For the primary analysis of primary efficacy variable 1, the MMRM implicitly imputes missing data under a missing at random assumption.

For the primary analysis of primary efficacy variable 2, participants for whom it cannot be ascertained that they are on statin therapy at the end of study will be assumed to have discontinued statin therapy (discontinued statin = 'yes').

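### SAP 2.5.1 counts every early terminator as a statin discontinuer whatever the records show; this is wider than the protocol's rule, is not reliably conservative for non-inferiority, and no visible analysis varies it

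*SAP*

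**What the plan says.** The second primary variable is statin discontinuation, tested for non-inferiority against a margin of 0.15 at one-sided 0.0125.

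- **SAP 2.5.1** compares the last statin end date with an assessment date (the Day 330 visit date minus 30 days), but only for completers who have that visit date. For the rest, "All early termination participants will be considered to not be on a statin for this endpoint", so they are coded as discontinued. The same code applies where "or they were a completer who did not have a Day 330 visit". Neither branch looks at the statin record.
- **Protocol 12.4.4** imputes discontinuation for "participants for whom it cannot be ascertained that they are on statin therapy at the end of study", and only for them. **SAP 2.5.4** keeps that narrower rule.
- **SAP Section 4** lists six changes from the protocol, among them dropping the interquartile range. This one is absent. The document history mentions only clarifications to 2.5.1.
- **Other data on statin use.** After study treatment stops, Protocol 9.1.1 says "the following data should be collected at clinic visits or via telephone/email contact", and new or concomitant treatments are on that list. Protocol 3 says eCRF data "will be complemented with EHR data and claims data (e.g., lipid measurements and concomitant medications", and Protocol 4.1 says "Eligible participants will need to consent to having health records made available"; Protocol 11.1 says only that such data may be used. After withdrawal of consent, Protocol 9.1.2 says "the data that would have been collected at subsequent visits will be considered missing".
- **Analyses of this variable beyond the primary one.** The visible ones are repeats in the Per-Protocol Set and Restricted Set 2 (SAP 2.5.2), subgroups (2.2.1), and a sensitivity analysis that drops participants whose IRT and CRF entries disagree (2.5.5).

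**The concern.** There are three linked problems.

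First, the passages conflict. They differ for anyone whose status near Day 330 can be established but who falls in one of the two automatic groups: someone who leaves after about Day 300 with a statin ongoing, a completer followed by telephone with no Day 330 visit date, or someone with usable health-record or claims data. The visit windows make the first case concrete. Under SAP Table 2-2 an exit visit on study days 301 to 375 supplies the Day 330 LDL-C value, yet a statin recorded as ongoing at that visit is coded as discontinued.

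Second, coding unknown status as an unfavourable outcome protects a superiority test better than a non-inferiority test. Adding the same event to both arms can pull the observed difference towards zero, which is the direction that passes the margin.

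Third, nothing visible tests whether the conclusion depends on this coding. Disposition by arm (SAP 2.3.1) and the statin-intensity shift table (SAP 2.4.2) give a partial view. Neither tests the margin or separates imputed from recorded discontinuations.

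**Working it through.** **Reproducing the plan.** Inputs from Protocol 12.8.1: rate 0.20 in each arm, margin 0.15, one-sided 0.0125 (z = 2.2414), power 0.90 (z = 1.2816).

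n per arm = (2.2414 + 1.2816)² × 2 × 0.20 × 0.80 / 0.15² = 176.5, so 177 per arm and 354 in total, as stated. Then 354 / 0.80 = 442.5, which gives about 444 in equal arms.

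**Set-up.** The primary set for this variable excludes statin-intolerant participants: 444 × 0.90 ≈ 400, or 200 per arm. Let p be an arm's true stopping rate, m the share with unknown status, and q the true stopping rate among those unknown.

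- Coded rate = p + m(1 − q).
- Bias in the difference = m_T(1 − q_T) − m_C(1 − q_C), with T inclisiran first and C usual care.

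The bias is zero if m and q match across arms. It favours non-inferiority if m is equal and q is higher on inclisiran, or if m is sufficiently higher in usual care. It is conservative if m is sufficiently higher on inclisiran.

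The error is the exact binomial probability that the Wald upper limit is at most 0.15 when the truth lies on the margin (0.35 vs 0.20). With no unknowns it is 1.26%.

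**Imputing discontinuation, all dropouts unknown (both wordings).** At the plan's 10% loss per arm with q equal to the arm's own rate, the coded rates are 0.35 + 0.10 × 0.65 = 0.415 and 0.20 + 0.10 × 0.80 = 0.280. The difference is 0.135.

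| Unknown, inclisiran / usual care | Coded rates | Error |
|---|---|---|
| 10% / 10% | 0.415 vs 0.280 | 2.65% |
| 9% / 11% | 0.4085 vs 0.288 | 5.2% |
| 8% / 12% | 0.402 vs 0.296 | 9.3% |
| 11% / 9% | 0.4215 vs 0.272 | 1.2% |
| 12% / 8% | 0.428 vs 0.264 | 0.5% |

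The unequal splits are illustrative and not from the documents. At 10%/10%, usual-care rates from 0.05 to 0.25 give 2.7 to 3.2% (1.2 to 1.6% with no dropout). If dropouts in both arms stop at a common rate, the error is 1.2 to 1.3%, which is no inflation.

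**The SAP's widening alone.** Suppose a share s of dropouts has ascertainable status, equal in both arms. The narrower rule then leaves m = 0.10(1 − s), and the error is 2.65%, 2.47%, 2.23%, 1.87% or 1.55% for s = 0, 10, 25, 50 or 75%. SAP 2.5.1 stays at 2.65% throughout, so over this range the widening adds 0 to 1.1 percentage points. If s differs by arm, the narrower rule also moves: 50% inclisiran/25% usual care gives 4.9%, and 25%/50% gives 0.7%. Reconciling the wording is therefore necessary but not sufficient.

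**Restricted Set 2.** This set removes inclisiran participants who missed a dose and keeps all usual-care participants, including terminators coded as discontinued. With 10% dropout per arm and own-arm stopping rates, the chance of declaring non-inferiority on the margin is:

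| Inclisiran terminators removed | n and coded rate, inclisiran (usual care 200, 0.280) | Probability |
|---|---|---|
| 10% | 198, 0.409 | 3.5% |
| 25% | 195, 0.400 | 5.4% |
| 50% | 190, 0.384 | 10% |
| 100% | 180, 0.350 | 29% |

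With equal stopping rates among dropouts (0.20 to 0.50) the four figures are 1.7%, 2.7 to 2.8%, 5 to 6% and 18 to 21%.

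**Power under true equality, 200 per arm.** It is 93% if the 0.20 planning rate already includes imputed cases. If it does not, the coded rate at 10% unknown is 0.20 + 0.10 × 0.80 = 0.28 in each arm, and power is about 87%.

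**The case against.** SAP 2.5.1 can be read as putting the protocol's rule into operation. The endpoint is anchored to an end-of-study visit, so someone without that visit has no assessment date. Participants who merely stop inclisiran stay on the visit schedule, so early terminators should mostly be consent withdrawals, losses and deaths, for whom the two rules largely agree. A statin listed as ongoing at an early exit does not show use in the final 30 days. This limits the reach of the conflict: the affected group may be small, and its size cannot be found from the documents. It does not remove the conflict, because SAP 2.5.1 never presents its rule as a definition of ascertainment and the late-exit case is miscoded on its face.

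Imputing discontinuation is also the protocol's own pre-specified choice, and the documents do not call it conservative. The 2.65% requires dropouts to keep the full 15-point difference between arms; with a 5-point gap (0.25 vs 0.20) the error is about 1.6%, and with none there is no inflation. That is correct, and it is why the claim is that the direction is unknown rather than that bias is certain.

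Restricted Set 2 is supportive only, and its 29% is a limiting case. Both points stand. It still cannot serve as a check on the coding, since it removes imputed events from one arm only.

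**Conclusion.** The concern holds and should be fixed. The textual conflict is certain: SAP 2.5.1 departs from Protocol 12.4.4 and SAP 2.5.4 on a primary endpoint, and Section 4 does not say so. The numerical effect is conditional. At the plan's 10% loss per arm the error ranges from no inflation (equal stopping rates among dropouts) to 2.65% (own-arm rates), and modest imbalance in loss takes it above or below the planned 1.25%. The documents neither support nor exclude these patterns. Most of the possible error comes from the imputation itself; the SAP's widening contributes at most about 1.1 points in the cases examined. The practical gap is that the visible outputs could not show whether a non-inferiority conclusion rests on recorded or imputed discontinuations. Redacted text could not be checked.

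**What to change.** 1. Align SAP 2.5.1 with Protocol 12.4.4 and SAP 2.5.4: use the recorded statin status wherever it establishes use in the assessment window, and impute discontinuation only otherwise. If the broader rule is kept, list it in SAP Section 4 with a reason. Either way, state how deaths and completers followed only by telephone are coded.
2. Pre-specify one tipping-point analysis of this variable that varies the coding of unknown status separately by arm. Report it as a bound, not a success criterion. Its extreme corner is severe: with 0.20 in both arms and 10% unknown in each, coding unknowns as discontinued on inclisiran (0.9 × 0.20 + 0.10 = 0.28) and as continuing in usual care (0.9 × 0.20 = 0.18) would meet the margin only about 15% of the time.
3. Report by arm how many discontinuations are imputed rather than recorded, in the primary set for this variable and in Restricted Set 2.
4. State whether the 0.20 planning rate includes imputed cases.

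The cost is SAP wording and modest programming, with no added participants or procedures. Items 1 to 3 carry the point; the coding of deaths and item 4 only supply missing detail.
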